# 12. Quality control and assurance: description of measures

The study will be submitted to the institutional review boards of all involved hospitals and will be registered in the Current Controlled Trials Database. Written informed consent will be obtained from all included patients or their legal representatives.

At its discretion, the study coordinating centre may conduct a quality assurance audit of this trial. If such an audit occurs, the investigator agrees to allow the auditor direct access to all relevant documents and to allocate his/her time and the time of his/her staff to the auditor to discuss findings and any relevant issues. A guideline for audit is available at the study coordinating centre.

In addition, regulatory agencies may conduct a regulatory inspection of this trial. If such an inspection occurs, the investigator agrees to allow the inspector direct access to all relevant documents and to allocate his/her time and the time of his/her staff to the inspector to discuss findings and any relevant issues.

# 12.1. Quality assurance and data/record keeping

The Sponsor is responsible for implementing and maintaining quality assurance and quality control systems with written SOPs and Working Instructions, at all sites. The PI is responsible for proper training of all involved study personnel.

All study related documents (essential documents and site documents) are archived at the local sites or electronically (electronic CRFs) for 10 years. On the stored CRFs, participants cannot be identified by name and birth date. Appropriate coded identification, will be used.t

All blood samples will be stored at the Kantonsspital Aarau for a maximum duration of 10 years and will then be destroyed.

# 13. Ancillary projects

# 13.1. Physio-pathological mechanisms of action of nutritional therapy

**Purpose:** To understand the physio-pathological mechanisms of action explaining how nutritional therapy exerts its effects on disease recovery in specific patient populations and illnesses. The large sample size and the diversity in medical diagnosis and comorbidities will offer the unique opportunity to study distinct effects of nutritional therapy.

**General approach:** Using patient data generated in the RCT, we will first look at how effects of nutritional therapy vary depending on age (quartiles), gender, medical illnesses (systemic infection, heart failure, renal failure, gastro-intestinal disease, tumor), BMI (<20, 20-25, >25-30, >30) and acuity (acute vs. chronic disease courses). We will also look at subgroups defined by admission nutritional / endocrine markers (e.g. initial pre-albumin, stress markers, inflammation blood biomarkers). In a second step, we will focus on specific patient populations to assess whether nutritional therapy has an effect on disease course. Specifically, we will focus on patients with systemic infections to study effects of nutritional therapy on the inflammatory response. We will look at biomarkers measured in blood samples collected from patients on admission and during follow up (inpatient days 0, 1, 3, 5 and 7). We will look at levels of inflammatory/infection biomarkers such as C-reactive protein (CRP) and PCT and stress markers such as cortisol and copeptin levels as surrogates for disease severity, recovery and medical outcome, respectively.

**Statistical approach:** Detailed methodology for the statistical analyses will be documented in a statistical analysis plan. To investigate whether differential treatment effects exist in patient subgroups as defined above, we will include interaction terms into the statistical model and check for effect modification (see details in RCT section, statistical approach). For subgroups defined by biomarker levels, we will divide those levels into quartiles to check for robustness of results. All analyses will be predefined based on biological plausibility to avoid multiple testing. We will further define a derivation sample and a validation sample (1:1) for these analyses for reproducibility of results and decreased risk of chance findings. We will use a linear mixed model approach to assess the effect of nutrition on serial biomarker levels over the course of hospitalization.

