# Synopsis

Sponsor / Sponsor- Investigator	[name]. med. [name]., MPH; Department of Endocrinology, Diabetes and Clinical Nutrition; University Department of Internal Medicine, Kantonsspital Aarau, [name]	
Study Title:	Full Title: Effect of Early Nutritional Therapy on Frailty, Functional Outcomes and Recovery of Undernourished Medical Inpatients Trial: The EFFORT Project	
Short Title	The EFFORT trial	
Protocol Version	EKNZ 2014_001 (version 3.3, 27.3.2014)	
Trial registration:	This trial will be registered at www.ClinicalTrials.gov	
Study category and Rationale	Category A (nutritional products used are authorised in Switzerland and the application is done according to the specialised information	
Clinical Phase:	Confirmation study regarding effectiveness and safety of nutritional therapy in medical inpatients	
Background and Rationale:	Illness is associated with appetite loss leading to relevant nutritional deficits, particularly in elderly, frail medical inpatients. Undernutrition is associated with morbidity, long hospital stays and costs. Despite these associations, benefit of providing early nutritional therapy to unselected medical inpatients at risk for undernutrition remains largely unproven due to lack of large-scale, high-quality randomized controlled trials (RCTs). Therefore, a large conclusive trial is urgently needed to answer the questions (a) whether or not appetite loss during acute illness is indeed a protective physiological response that should be tolerated; (b) which patients do or do not benefit from nutritional therapy; (c) how and why nutrition affects the course of disease from a mechanistic physio-pathological standpoint.	
Objective(s):	To test the hypothesis that in medical inpatients at risk for undernutrition defined by the nutritional risk score (NRS 2002), early tailored nutritional therapy to reach nutritional targets based on individualized nutritional counseling is a cost-effective strategy to prevent mortality, morbidity and functional decline.	

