Importantly, data from critical care cannot unconditionally be transferred to medical inpatients with a lower degree of disease severity. Still, the above-mentioned conflicting observations re-emphasize that nutritional therapy is a medical intervention with associated risks and costs, and call into question todays nutritional approach in medical inpatients. The current lack of strong guideline recommendations for type, caloric amount and timing of nutritional therapy in acutely-ill medical inpatients outside critical care is mainly explained by the paucity of high-level evidence showing such therapy's efficacy, safety and cost benefits, and the absence of knowledge regarding which patient population do or do not benefit. Hence, evaluation of efficacy, safety and possible cost benefits within a large, well-controlled conclusive RCT is warranted to assess the effects of early nutritional therapy on patient outcomes in the medical inpatient setting. The EFFORT trial will not only answer the question about overall benefit or harm, but using a physio-pathological mechanistic approach, it also will explore and provide conclusive answers about whether, why, how, and in which patient populations nutritional therapy does or does not works.

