# 4.3. Randomization and study procedures

If patients fulfill all inclusion criteria, with no exclusion criteria and provide informed consent, they will be randomized in a 1:1 fashion into the intervention group or the control group according to a pre-specified, computer-generated, web-based randomization scheme using the secuTrial© Software (managed and secured by the Clinical trial Unit of the University of Basel). The randomization will be stratified for the site and initial NRS (Appendix 2). In both study groups, all patients will be re-assessed daily by the nutritional specialist to re-evaluate nutritional intake and whether nutritional targets are met. If patients in the intervention group do not reach the nutritional targets (<75%), their nutritional strategy will be escalated according to the nutritional guidelines.

We will systematically collect blood samples at admission (day 0) and on inpatient days 2, 4, 6 and 8 for later batch measurement of nutritional markers and other biomarkers. If clinically indicated, there will be pre-prandial measurement of blood glucose levels 4 times daily and insulin treatment in all patients as part of usual clinical practice. There will also be regular measurement of nutritional factors in blood and possibly 24 hour urine to assess the effectiveness of nutritional therapy (see CRF for further details).

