# 8.2. Statistical approach

Detailed methodology for summaries and statistical analyses of the data collected in this study will be documented in a statistical analysis plan. The statistical analysis plan will be finalized before database closure.

Briefly, a consort diagram will be reported including all screened patients, patients lost to follow up and patients included in the final analyses. Primary and secondary endpoints will be compared between trial arms in the overall ITT population and within predefined subgroups as discussed below. All outcomes will be analyzed in an uncorrected manner as well as jointly corrected for the main risk factors (Barthel's index at baseline, study center and initial NRS categories). For our primary analysis, we will compare the two arms with a chi-square test and we will also estimate effect size with a logistic regression model reporting unadjusted and adjusted odds ratios (OR) and corresponding 95% confidence intervals (CIs).

We will do different predefined subgroup analyses by including interaction terms in the regression models to test for effect modification by important baseline factors. Specifically, we will look at patients age (<60, 60-75, >75 years), gender, risk for undernutrition stratified according to initial NRS (3, 4, >4 points), BMI (<20, 20-25, >25-30, >30), main medical diagnosis (systemic infection, heart failure, acute renal failure, gastro-intestinal disease, tumor), comorbidities (diabetes, chronic renal failure).

For the analysis of functional outcome (defined by Barthel's index) we will use a non-parametric Wilcoxon rank sum test to compare Barthel's index at day 30 between randomization arms. However, to adjust for additional variables, we will also fit a multivariate linear model including Barthel's index at baseline, study center and initial NRS to estimate effect size and 95% confidence intervals (95%Cls). If needed, data will be transformed as appropriate (e.g., log transformation). Moreover, we will assess the progression of Barthel's index over time (i.e. admission, day 8, day 30) using a linear mixed model approach to account for the repeated measurements per patient.

A similar approach will be used for all other secondary endpoints where we will use chi-square tests / logistic regression analysis for binary outcomes, Wilcoxon rank sum test / linear models for continuous outcomes and log-rank test / cox regression for time-to-event data as appropriate.

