#### 8.3. Sample Size considerations

This study is designed to show superiority of nutritional therapy compared to "appetite-guided" standard care regarding the composite primary endpoint. Our hypothesis is that early nutritional therapy will reduce mortality and morbidity within a follow up period of 30 days after the index hospitalization. From preliminary observational data collected during the TRIAGE pilot study, we estimate that 40% of the target patient population (NRS ≥3 points and LOS ≥5days) will reach the primary endpoint within 30 days (10% mortality, 5% ICU admission from the hospital ward, 15% complications, 10% functional decline with 10% reaching more than 1 endpoint). We hypothesize that our nutritional intervention will decrease this risk by an absolute number of 6% (relative decrease of 15%), i.e., from 40% to 34%. For a comparison of two independent binomial proportions using Pearson's Chi-square statistic with a Chi-square approximation with a two-sided significance level of 0.05, a sample size of 1'359 per group achieves a power of at least 0.9 when the proportions are 0.4 and 0.34.

Thus, a total number of 2000-3000 patients will provide the study with a power of 78-90% to detect a 15% relative decrease in the risk to reach the primary endpoint. The table below shows sample sizes for different assumptions regarding effectiveness of our intervention and power.

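### Section 13.1 wrongly treats predefinition as a remedy for multiple testing, and the promise of conclusive subgroup answers exceeds what the planned interaction tests can deliver

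*Protocol*

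**What the plan says.** Section 8.2 of the protocol sets the main-trial subgroup analysis: "Primary and secondary endpoints will be compared between trial arms in the overall ITT population and within predefined subgroups as discussed below". The method then given is interaction terms in the regression models, for age, gender, initial NRS, BMI, main medical diagnosis (five named) and comorbidities (two named). No significance level and no multiplicity rule is given for these tests.

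Section 13.1, an ancillary project, covers much of the same ground. It adds acute versus chronic course and an open, example-only list of admission marker subgroups. Its statistical paragraph says: "All analyses will be predefined based on biological plausibility to avoid multiple testing". The next sentence sets up a 1:1 derivation and validation sample for these analyses, to aid reproducibility and reduce chance findings. It does not say what counts as validated.

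Section 2.2 says the trial will "provide conclusive answers about whether, why, how, and in which patient populations nutritional therapy does or does not works". The Synopsis lists "which patients do or do not benefit from nutritional therapy" among the questions that call for a large conclusive trial.

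The only significance level stated is in section 8.3, for the primary comparison of event rates of 40% and 34%: "with a two-sided significance level of 0.05, a sample size of 1'359 per group achieves a power of at least 0.9".

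**The concern.** Multiplicity depends on how many tests are run and how they are read, not on when they were chosen. Listing analyses in advance on biological grounds guards against picking subgroups after seeing the data. It does not change the chance that at least one of the listed tests is positive by accident. A protocol that says otherwise invites its authors to treat the problem as solved.

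This matters because of the promise attached. If subgroup results are to be conclusive in both directions, a chance interaction could be reported as proof that some patients benefit and others do not, and an undetected interaction as proof that all respond alike. The trial is sized for one overall comparison, not for either statement. Section 8.2 also applies the subgroup comparisons to secondary as well as primary endpoints, so the number of tests grows further.

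**Working it through.** **Inputs from the protocol.** Event rates 0.40 and 0.34; two-sided 0.05 for the primary comparison; 1359 per group for power 0.9; "a total number of 2000-3000 patients will provide the study with a power of 78-90" per cent (all section 8.3); allocation 1:1 (section 4.3). Subgroup factors from section 8.2: age, gender, NRS, BMI, main diagnosis and comorbidities make 6. Testing the diagnoses and comorbidities singly gives 4 + 5 + 2 = 11.

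**Assumptions, not in the protocol.** Each interaction is tested at 0.05; tests are independent; one endpoint; no true effect modification for the error rates. For power, the modifier divides patients 50:50.

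**1. The plan's own figure.** With mean proportion 0.37,

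n = [1.960 × √(2 × 0.37 × 0.63) + 1.282 × √(0.40 × 0.60 + 0.34 × 0.66)]² / 0.06² = 1358.6, so 1359 per group.

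This matches section 8.3. The total is 2718. Power is 79.4% at 2000 patients and 92.6% at 3000, so the overall comparison is adequately sized.

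**2. Chance of at least one false interaction, no split.** The formula is 1 − 0.95^k.

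- k = 6: 1 − 0.95^6 = 0.265
- k = 11: 1 − 0.95^11 = 0.431

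Positive correlation between tests lowers these figures. Adding secondary endpoints raises them.

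**3. The same with the split.** If a finding had to reach 0.05 in both halves (one possible criterion; the protocol states none), each test has error 0.05² = 0.0025.

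- k = 6: 1 − 0.9975^6 = 0.015
- k = 11: 1 − 0.9975^11 = 0.027

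So the split can control the error well, provided a criterion of this kind is fixed and the split applies to the analysis in question.

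**4. Power for an interaction.** Take a 6-point effect in one half of the patients (0.40 vs 0.34) and none in the other (0.40 vs 0.40). The difference in risk differences is 0.06. With four cells of N/4 patients each,

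SE = √[(0.24 + 0.2244 + 0.24 + 0.24) / (N/4)], and power ≈ Φ(0.06/SE − 1.960).

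| N | SE | Power, full sample | Power, one half | Power, both halves |
|---|---|---|---|---|
| 2000 | 0.0435 | 28% | 16% | 2.6% |
| 2718 | 0.0373 | 36% | 21% | 4.2% |
| 3000 | 0.0355 | 39% | 22% | 4.9% |

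For an interaction twice as large (12 points in one half, none in the other), power in the full sample is 80% at 2000 and 93% at 3000. Requiring both halves brings this down to 26% and 46%.

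**5. Reading.** Without the split, the 8.2 tests carry a material false-positive risk and modest power for a modifier as large as the whole planned effect. With the split, false positives become rare but a modifier of that size would nearly always be missed. Neither supports conclusive statements in both directions.

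**The case against.** The strongest reply is that the protocol does have a safeguard. The split stands directly after the sentence at issue, applies to the 13.1 analyses, and those overlap heavily with the 8.2 factors. If significance in both halves were required, family-wise error for 6 to 11 tests would be about 1.5% to 2.7%. This stands, and a reader who infers that the subgroup family is wholly uncontrolled goes beyond the text. What remains is that the split has no success criterion, is not stated for 8.2, and makes conclusive answers harder to reach because of its cost in power.

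Second, a reader might infer that every subgroup is tested at the full 0.05. The protocol sets that level only for the primary comparison. The 26% to 43% is therefore conditional, and since it is below one half it does not make a false subgroup claim likely.

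Third, details are left to a statistical analysis plan that is not shown. A multiplicity rule or exploratory label may be there, so their absence from the protocol is not the point. A later plan would not, however, correct the wrong reasoning in 13.1 or the promise in 2.2.

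Fourth, a reader might infer that a non-significant result within one subgroup would be reported as no benefit. Section 8.2 does speak of comparisons within subgroups, but the method it then describes is the interaction test, and nowhere does it state such a reading. Figures for within-subgroup significance would also need subgroup sizes that the protocol does not give. They are not used here.

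Finally, section 2.2 speaks of exploring as well as concluding, the Synopsis item is background rather than an analysis claim, and section 13 is labelled ancillary. This softens the tone, but the commitment to conclusive answers by patient population remains.

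**Conclusion.** The point holds as one about stated reasoning and about what may be concluded. The sentence in 13.1 is wrong, and the promise in 2.2 is not supported by the design. Under independent tests at 0.05 and one endpoint, the 8.2 family has about a 26% to 43% chance of at least one false interaction; correlation lowers this. A 50:50 modifier equal to the full planned effect has about 36% to 39% power at 2718 to 3000 patients, and about 4% to 5% if both halves must be significant. A modifier twice as large could be detected in the full sample, so subgroup work is worth doing; it is the word conclusive that fails.

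The documents do not support the stronger readings that the family is uncontrolled or that a false subgroup claim is likely. The primary analysis, the sample size and the overall conclusion are unaffected.

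**What to change.** - In 13.1, delete the closing clause of the sentence on predefinition, which presents it as a way round multiple testing. Predefinition can stay, described as a limit on data-driven choice.
- In 8.2 and 13.1, state that subgroup results are exploratory and judged by the interaction test, with estimates and confidence intervals for each subgroup but no within-subgroup p-values.
- State what a finding must show in the validation sample to count as validated, and whether the split also covers the 8.2 subgroups.
- In 2.2, replace the conclusive wording for patient populations with hypothesis-generating wording, and keep the Synopsis consistent with it.

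A formal family-wise procedure such as Holm is an option if any subgroup claim is meant to be confirmatory, but it trades away power and is not needed if the results are exploratory. The change is to wording only and needs no extra patients or data. The cost is that the trial claims less about who benefits.

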# 13.2. Cost-effectiveness analysis of nutritional therapy

**Purpose:** to perform a cost-effectiveness calculation for early nutritional therapy in medical inpatients at risk for undernutrition including cost-effectiveness and cost-utility analyses. These analyses will be from the health-care payers' perspective using intervention data generated in the RCT.

**General approach:** The total cost calculation will include nutritional costs (including nutritional products and estimated time of dieticians spent with patients) and all medical costs within 30 days after study inclusion. The total cost calculation also will include all hospitalisations after index hospitalisation. We

will derive estimates of the real costs using REKOLE a comprehensive accounting algorithm used by Swiss hospitals to internally compute provider costs. Cost-effectiveness will be expressed as the incremental cost-effectiveness ratio. Non-parametric bootstrapping will be used to estimate 95%Cls for differences in incremental costs and effects. We will further calculate the probability value that nutritional therapy is cost-effective for a range of different willingness to pay values. We will define confidence intervals for the relevant cost difference. We will assume equivalence if the difference in total direct costs will lie between the equivalence margins. Non-inferiority of costs will be demonstrated if the upper limit of the confidence interval for cost differences between the two strategies will be smaller than the cost difference. In a second step we will perform a joint analysis of effects and costs in a cost-utility analysis by analysing the cost per quality adjusted life years (QALY) gained. We will present an overall analysis, and different subgroup analyses as defined in the RCT. Specifically, we will look at patients age (<60, 60-75, >75 years), gender, risk for undernutrition stratified according to initial NRS (3, 4, >4 points), main medical diagnosis (systemic infection, heart failure, acute renal failure, gastro-intestinal disease, tumor), comorbidities (diabetes, chronic renal failure), LOS (<8 days, ≥8 days) and BMI (<20, 20-25, >25-30, >30).

**Presentation of results:** To assess the shape of the joint sampling distribution of costs and effects we will present the joint density distribution of incremental costs and effects on the cost-effectiveness plane.

We will further estimate the incremental net monetary benefit and the uncertainty surrounding this estimate. We will visualise the uncertainty surrounding the cost-effectiveness estimates by deriving the cost-effectiveness acceptability curves. These curves provide estimates of the probability that the intervention is cost-effective for a range of different willingness to pay values (*Figure 3*).

Because acceptability curves focus on the incremental cost effectiveness ratio as a continuous

Figure 3: Visualization of cost-effectiveness

156.215

-269.963

-117.552

Effect difference

336341

measure in relation to the amount a policymaker is willing to pay to gain one unit of effect, acceptability curves have no meaningful interpretation in economic noninferiority research. We will therefore define cost and effect margins (based on the cost difference for one day of hospitalisation and based on an effect difference of 2 points for QoL in the EuroQol Score) for a non-inferiority scenario in case we cannot show superiority in costs and comparable effects of the two investigated management strategies under investigation. Finally the uncertainty around the treatment decision will be expressed in terms of the total expected value of perfect information.

**Outlook**: No prospective trial data are available for incremental cost-effectiveness of nutritional therapy in a large unselected population of medical inpatients outside critical care. This analysis will provide

conclusive evidence about expected costs and benefits of nutritional therapy in different types of medical patients for more rational decision-making of healthcare providers.

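### In the ancillary cost analysis, the equivalence rule ignores the confidence interval and the non-inferiority rule names no margin

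*Protocol*

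**What the plan says.** All the relevant text is in Protocol section 13.2, one of the ancillary projects in section 13.

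Under General approach, the plan first fixes the method and level of the intervals: "Non-parametric bootstrapping will be used to estimate 95%Cls for differences in incremental costs and effects". It later adds: "We will define confidence intervals for the relevant cost difference". The two decision rules follow directly:

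- Equivalence: "We will assume equivalence if the difference in total direct costs will lie between the equivalence margins".
- Non-inferiority of costs is shown if "the upper limit of the confidence interval for cost differences between the two strategies will be smaller than the cost difference".

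Under Presentation of results, the plan returns to non-inferiority as a fallback, in case superiority in costs with comparable effects cannot be shown. There it says: "We will therefore define cost and effect margins". The cost margin is to be "based on the cost difference for one day of hospitalisation". This text neither restates nor amends the two rules.

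**The concern.** An equivalence claim has to allow for the uncertainty of the estimate. A rule that looks only at whether the difference lies between the margins treats a noisy estimate and a precise one alike, and total costs are usually noisy and skewed.

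The non-inferiority sentence has a different fault. It compares the upper limit of an interval for a difference with something called the cost difference. If that is the estimated difference, the condition contradicts itself, because the upper limit lies above the estimate. The quantity that belongs there is a margin.

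Taken as printed, one claim is too easy to make and the other is out of reach. An analyst would have to reinterpret both rules, possibly after seeing costs by arm. Cost-effectiveness is part of the overall hypothesis in section 3.1, so the criteria should be usable as written.

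**Working it through.** The Protocol gives no power or error rate for the cost rules, so there is no figure of its own to reproduce here. As a check on the group sizes used below, the standard two-proportion formula with pooled variance and two-sided 0.05 reproduces all nine entries of the table in section 8.3, for example 1359 per group for 0.40 against 0.34 at 90% power.

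**Inputs**

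- Interval: 95%, non-parametric bootstrap (13.2).
- Sample size: "a total number of 2000-3000 patients" (8.3) at 1:1 allocation (4.3), so n = 1000 to 1500 per group.
- Assumptions, because the Protocol gives no standard deviation of costs and no margin amount: symmetric margins ±M with M between 0.05 and 0.30 SD, and a normal approximation with SE = SD × √(2/n).

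For n = 1000, SE = √(2/1000) = 0.0447 SD, so M = 0.05 SD is 1.12 SE. For n = 1500, SE = 0.0365 SD, so M = 0.30 SD is 8.22 SE.

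**Equivalence, true difference exactly at M**

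- As written: P = Φ(0) − Φ(−2M/SE). At M = 1.12 SE this is 0.487. At M = 2.24 SE and above it is 0.500 to three decimals.
- Whole 95% interval inside ±M: P = max{0, Φ(−1.96) − Φ(1.96 − 2M/SE)}, which is at most 0.025. With a 90% interval the cap is 0.05.
- As written, with the true difference one SE beyond M: about Φ(−1) = 0.16.

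Over n = 1000 to 1500 and M = 0.05 to 0.30 SD, the rule as written gives 0.49 to 0.50 at the margin.

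**Non-inferiority as written**

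A normal-theory upper limit is the estimate plus 1.96 SE. It is below the estimate only if 1.96 SE < 0, which is impossible. A percentile bootstrap limit was also checked by simulation with assumed skewed costs (lognormal, log-mean 9.5, log-SD 0.8, same distribution in both arms, 1000 per arm, 500 resamples). The condition was met in 0 of 300 simulated trials.

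**What interval-based rules would do**

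Under the same assumptions with n = 1359 per group and a true difference of zero, the chances of each claim are 2Φ(M/SE) − 1 for equivalence as written, max{0, 2Φ(M/SE − 1.96) − 1} for equivalence by the 95% interval, and Φ(M/SE − 1.96) for non-inferiority against M:

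| M (SD) | M/SE | Equivalence as written | Equivalence, 95% interval | Non-inferiority against M |
|---|---|---|---|---|
| 0.05 | 1.30 | 0.81 | 0 | 0.26 |
| 0.10 | 2.61 | 0.99 | 0.48 | 0.74 |
| 0.15 | 3.91 | >0.99 | 0.95 | 0.97 |
| 0.20 | 5.21 | >0.99 | >0.99 | >0.99 |

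At a true difference of M, the chance of a non-inferiority claim is Φ(−1.96) = 0.025.

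**The case against.** The strongest reply is that both sentences are loosely worded and the intent is sound. Just before the rules, the plan speaks of a relevant cost difference, and Presentation of results describes the margin with the same noun: "define cost and effect margins (based on the cost difference for one day of hospitalisation". On that reading, the non-inferiority sentence compares the upper limit with the margin, which is the standard rule. This is plausible and probably what was meant. A reader might infer from the literal wording that non-inferiority has no chance of being shown in this trial. The documents do not support going that far, since a condition that cannot be met would be recognised as a slip. What stands is that the rule does not name the margin and one sentence would use nearly the same term for two different quantities.

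For equivalence, the reply is that intervals are announced in the preceding sentence and were surely meant to be used. This is weaker: the rule itself tests the difference, and nothing ties the interval to it. The margin reading does not rescue this half.

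It is also fair to say that the 50% and 16% are general properties of a point-estimate rule at chosen true differences. They do not say how likely a false equivalence claim is in this trial, which depends on cost variability and a margin amount that the Protocol does not give.

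Two further complaints would be misplaced. The interval level is not missing, because 13.2 gives 95%. The margin's amount can be left to the statistical analysis plan, which section 8.2 says will be finalised before database closure.

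**Conclusion.** The point holds, at minor to moderate weight. The equivalence rule as written omits the interval. With the true difference at the margin it would declare equivalence about half the time (0.49 to 0.50 for 1000 to 1500 per group and an assumed margin of 0.05 to 0.30 SD), against at most 2.5% with the 95% interval. The non-inferiority rule is unusable if read literally and sound if the one-hospital-day margin is read into it. The two parts of 13.2 need to be reconciled.

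A reader might infer that the cost-effectiveness question in section 3.1 cannot be answered. That does not follow. The incremental cost-effectiveness ratio with its bootstrap intervals, the cost per quality-adjusted life year, net monetary benefit and acceptability curves do not rest on these two sentences, and non-inferiority is only a fallback. Costs are not among the endpoints in section 4.2 and do not enter the sample size in 8.3.

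The figures rest on a normal approximation and symmetric margins. The impossibility of the literal non-inferiority rule for a normal-theory interval needs no assumption about the size of the costs.

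**What to change.** Replace the two rules in 13.2 with wording such as this:

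*Equivalence of costs is concluded only if the whole 95% bootstrap confidence interval of the difference in total direct costs lies within the equivalence margins. Non-inferiority of costs is concluded if the upper limit of that interval, for intervention minus control, is below the cost margin based on one day of hospitalisation. The margins are set before costs are compared by arm.*

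The amount can be recorded in the statistical analysis plan. If a 90% interval is preferred for equivalence, this should be stated, with the 5% error at the margin that goes with it.

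The change is two rewritten sentences and one on timing, with no new data or patients. The real cost is fewer equivalence claims. At a true difference of zero with 1359 per group, the chance falls from 0.99 to 0.48 if the margin is 0.10 SD, and hardly changes at 0.20 SD. At 0.05 SD the 95% interval is too wide to fit inside the margins, so equivalence could not be shown.
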